## 1.0 Objectives / Specific Aims

The goal of this work is to develop, systematically evaluate, and clinically test an integrated cessation intervention comprised of a depression-specific Behavioral Activation (BA) for cessation mobile app (“Goal2Quit”) packaged with nicotine replacement therapy (NRT) sampling. This integrated intervention will address the need for an easily disseminable, evidence-based, depression-specific cessation intervention for delivery via primary care.

**Aim 1:** We will first develop Goal2Quit consistent with the BA for smoking cessation manual(1) and will complete usability testing of the app with depressed smokers (N=10) engaged with primary care.

**Aim 2:** We will then refine the app and preliminarily test the integrated intervention via a single-arm feasibility test (N=10) followed by individual interviews to address potential pitfalls. Goals of feasibility testing include assessment of: 1) access, 2) user feasibility/acceptability, 3) engagement and retention, 4) adherence, and 5) NRT utilization.

**Aim 3:** Upon further refinement, we will then conduct an RCT (N=150, followed for 12 weeks) of Goal2Quit+NRT Sampling as compared to treatment as usual (TAU) among primary care engaged adults with primary objective to provide effect size estimates for a larger RCT.

**Hypotheses:** Participants randomized to Goal2Quit+NRT Sampling, compared to TAU, will have greater (numerically, if not statistically) decreases in depressive symptoms as well as superior cessation-related outcomes (motivation to quit, confidence in quitting, quit attempts/quit duration). Secondary outcomes include all those listed in Aim 2.

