**Small-Scale RCT.** A two-arm RCT (N=150) will test the efficacy of Goal2Quit+NRT Sampling vs. TAU. See above for inclusion/exclusion criteria. After completing determination of eligibility, reviewing study procedures, completing informed consent, and completing baseline assessments, if eligible, the participant will be randomized 2:1 to either Goal2Quit + NRT sampling or TAU. Participants randomized to Goal2Quit + NRT sampling will be provided with their intervention in the same manner as feasibility testing participants. TAU participants will be mailed a package that includes only 1) NCI’s “Clearing the Air” booklet, which includes information on quitting smoking, and 2) Information on study participation, including the schedule of follow-up assessments and compensation. Participants will subsequently be emailed a REDCap link (accessible via smartphone, tablet, or computer) to complete follow-ups weekly for 8 weeks, with an additional follow-up at Week 12.

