**Assessments:** Assessments are estimated at 20 minutes each and will be administered remotely via REDCap through our established procedures. Participants will be sent an email and/or SMS text each week with a link to access their REDCap surveys. SMS text messaging is possible via Twilio, embedded within our RedCap system, which allows participants to complete a survey directly from their phone, without having to access a webpage. Note that surveys are not completed via texting, just prompted via text with link to RedCap. Participants can choose to receive their weekly surveys via email if they wish, again with a link to a secure RedCap survey. Participants will be compensated \$10 in cash and/or electronic gift codes (e.g., Amazon) for completion of each and will receive a \$20 bonus if at least 2/3 are complete. Participants will also receive a second bonus of \$20 for completing all follow up surveys. To help with retention, the last 20-25 participants enrolled will receive a signed letter from the study team and a few small items with the study’s logo (e.g., pen, flash drive, coaster, t-shirt) from the study team at random time points throughout their participation as a thank you for joining. Cigarette smoking, use of other tobacco products (e.g., e-cigarettes), and quit attempts/quit duration will be assessed at each follow-up using a timeline followback for the last 6-months at baseline and since prior follow-up for each subsequent assessment(71, 72). Nicotine dependence will be assessed at baseline via the Fagerstrom Test of Nicotine Dependence(73). Participants will report motivation to quit and confidence in quitting using a modified Contemplation Ladder(74). Depressive symptomatology will be assessed via both the PHQ-8(64) and the Beck Depression Inventory-II (BDI-II)(75). The PHQ-8 is briefer than the BDI-II, and thus will determine study eligibility. The BDI-II will be administered at all time points to determine change in symptoms. We will assess and track psychiatric medication use over time and will stratify randomization based on medication use. Adequate procedures are in place to assess for and protect against the potential for suicidal ideation (see Protection of Human Subjects). Process-related variables including activation, assessed via the activation subscale of the Behavioral Activation for Depression Scale(76), and environmental reward, assessed via the Reward Probability Index(77) will be assessed at baseline and all follow-ups to examine potential treatment mechanisms. Treatment adherence will reflect both Goal2Quit and NRT utilization. Regarding Goal2Quit, adherence will be measured based on 1) download of Goal2Quit (yes/no) and 2) analytic data including: number of logins, duration of sessions (average per session and cumulative), rolling retention, number of activities scheduled, and percent completed activities. Regarding NRT utilization, participants in both groups will be queried at all follow-ups for: 1) use of NRT since the last assessment, 2) purchase of NRT since the last assessment, and 3) perception of NRT products via the Attitudes Toward NRT Scale(78). Engagement in other cessation (other medications, behavioral treatment, quitlines) and mental health (medications, therapy) treatments will also be assessed. Feasibility and acceptability will be assessed for those in the Goal2Quit+NRT Sampling condition during each assessment. Participants will be prompted to

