## 11.0 Data Management

As this is a pilot trial, our primary goal is to determine feasibility/acceptability and estimate an intervention effect size. To estimate an effect size for the Goal2Quit+NRT Sampling intervention, we will randomize participants 2:1 (active:control), with 100 participants in the active condition and 50 in the control condition. Assuming a quit attempt rate (point prevalence) of 40% in the active condition and 15% in the control(59), with 2:1 randomization we will have 60% power to detect an effect; again our intent is not a fully powered trial. To further account for attrition (assumed to be 20% across groups), we will recruit 180 participants total. For this pilot RCT, with a 22-month enrollment period, subtracting three months for final study participants, we fully expect to feasibly recruit 9-10 participants per month (180 participants/19 months).

Data analysis will focus on descriptive analysis of changes over time in depressive symptoms and cigarette smoking by condition. Considering the relatively small sample, possible missing data, and repeated measures, we will fit the longitudinal data with Hierarchical Linear Modeling (HLM) to fully use available data(80). With HLM, we can estimate and model the degree of relatedness of our observations within the same treatment condition and within the same individual, thereby correctly estimating standard errors and eliminating the problem of inflated Type I error(81). First, we will assess patterns of missing data, research dropout, and distributional properties of all measures. Then, effects of the Goal2Quit+NRT Sampling intervention as compared to TAU on cigarette smoking (motivation to quit, confidence in quitting, and quit attempts/quit duration) and depressive symptoms over time will be examined using HLM. Planned covariates will include sex and baseline levels of depression and nicotine dependence as well as the main effect of time.

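### Quit attempts get the same HLM as depressive symptoms although their records cover about 7 and then about 28 days, with no offset or common window, and no by-arm quit-attempt proportion over a defined period is specified

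*Combined protocol and SAP*

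**What the plan says.** All references are to the combined protocol and SAP.

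- **Model (11.0 Data Management).** Motivation, confidence, quit attempts/quit duration and depressive symptoms share one sentence: "quit attempts/quit duration) and depressive symptoms over time will be examined using HLM". No distribution, link, offset or analysis window is given. On covariates: "Planned covariates will include sex and baseline levels of depression and nicotine dependence as well as the main effect of time".
- **Recording (10.0, Assessments).** Smoking and quit attempts come from a "timeline followback for the last 6-months at baseline and since prior follow-up for each subsequent assessment".
- **Schedule (10.0, Small-Scale RCT, and the assessment table).** Participants "complete follow-ups weekly for 8 weeks, with an additional follow-up at Week 12".
- **Design rate (11.0).** "Assuming a quit attempt rate (point prevalence) of 40% in the active condition and 15% in the control". No period or time point is attached, and a quit attempt is not defined.
- **Description (11.0).** "Data analysis will focus on descriptive analysis of changes over time in depressive symptoms and cigarette smoking by condition". No quit-attempt proportion is named.
- **Purpose (1.0, Aim 3).** The RCT has the "primary objective to provide effect size estimates for a larger RCT".

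**The concern.** The BDI-II and the Contemplation Ladder are not described as recorded since the last survey, so survey spacing does not define what they measure. A quit-attempt record is different: the chance of at least one attempt, and the number of attempts, grow with the days covered. Over the planned schedule the last record covers four times as many days as each of the others. A linear model with no exposure term reads that extra time as more quitting, and more so in the arm with the higher rate.

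Separately, the quantity used for power is a proportion with a quit attempt, but no period defines it and no analysis is stated to return it. Since the RCT exists to supply an effect size, a later trial could be sized on a per-survey difference, a cumulative difference or something between, all from the same data.

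**Working it through.** **1. The plan's own figure.** The stated power is 60% for 40% versus 15% at 100:50. Alpha is not stated; I assume two-sided 0.05. Pooled proportion = (40 + 7.5)/150 = 0.3167. Null SE = sqrt(0.3167 × 0.6833 × (1/100 + 1/50)) = 0.0806. Alternative SE = sqrt(0.40 × 0.60/100 + 0.15 × 0.85/50) = 0.0704. z = (0.25 − 1.96 × 0.0806)/0.0704 = 1.31, so power is about 90.5%. The stated figure does not reproduce. That is a separate matter, and nothing below uses it.

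**2. Days covered (10.0).** With complete surveys there are eight records of about 7 days and one of about 28: 8 × 7 + 28 = 84 days.

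**3. Arm difference per record.** Assume a constant attempt rate. If p is the proportion with any attempt over T weeks, then P(any attempt in t weeks) = 1 − (1 − p)^(t/T). Take T = 12:

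- 7-day record: 1 − 0.60^(1/12) = 4.17%; 1 − 0.85^(1/12) = 1.35%; difference 2.82 points.
- Week 12 record: 1 − 0.60^(4/12) = 15.66%; 1 − 0.85^(4/12) = 5.27%; difference 10.38 points (unrounded inputs).

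Behaviour is identical throughout; only the window changes.

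**4. What a linear model makes of it.**

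- Average over nine records: (8 × 2.82 + 10.38)/9 = 3.66, against 2.82 for twelve equal weekly windows; ratio 1.30.
- Trend: the survey weeks 1–8 and 12 have mean 48/9 = 5.33 and sum of squares 348 − 48²/9 = 92. Only Week 12 departs from 2.82, so the least-squares slope of the arm difference is (12 − 5.33) × (10.38 − 2.82)/92 = 0.55 points per week. The true slope is zero.

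**5. Relative effect.** Average record, active: (8 × 4.168 + 15.66)/9 = 5.44%. Control: (8 × 1.345 + 5.27)/9 = 1.78%. The ratio is 3.06, against 4.168/1.345 = 3.10 for weekly windows. For counts, the rate ratio is ln(0.60)/ln(0.85) = 3.14 whatever the window.

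**6. The unstated period.** This table is only an illustration under a constant attempt rate, using the formula in step 3. Entries are arm differences in percentage points.

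| 40%/15% read as any attempt in | 7-day record | Week 12 record | Mean of nine records | By Week 12 |
|---|---|---|---|---|
| 12 weeks | 2.8 | 10.4 | 3.7 | 25.0 |
| 8 weeks | 4.2 | 14.7 | 5.3 | 31.9 |
| 28 days | 8.0 | 25.0 | 9.9 | 39.8 |
| 7 days | 25.0 | 39.2 | 26.6 | 14.0 |

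**7. The direct estimate.** At 40% versus 15% and 100:50, the risk difference is 25 points with 95% CI 25 ± 1.96 × 7.04 = 11.2 to 38.8. If all 180 recruited were randomised 120:60, the SE is sqrt(0.24/120 + 0.1275/60) = 0.0642 and the CI is 12.4 to 37.6.

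**The case against.** **The recall span is not necessarily the unit of analysis.** A timeline followback is a calendar method. Successive spans join into one 12-week calendar, which can be cut into equal windows or summarised as any attempt by Week 12. Nowhere is one record per survey named as the modelled unit. This stands, and makes the distortion conditional. But the plan does not say that the calendar will be re-cut, and per-survey entry is a natural reading of a repeated-measures HLM.

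**The 1.30 is largely a change of unit.** Nine records over 84 days average 84/9 = 9.3 days, and 9.3/7 = 1.33. This also stands. With complete surveys the windows match across arms at every visit, so the ratio barely changes on the 12-week reading. It shifts somewhat more on the 7-day reading (45.2/18.6 = 2.43 against 40/15 = 2.67).

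**The 12-week reading sits awkwardly with the point-prevalence label.** On a 7-day reading the per-record difference is already near 25 points. That reading, however, implies 99.8% versus 85.8% attempting by Week 12. A constant rate is itself doubtful, since the app suggests a quit date within three weeks and the NRT supply lasts two. The figures show direction and scale; they do not forecast.

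**The plan checks distributions first.** It does, but ties no alternative model to the result, and a distribution check does not equalise exposure. A time term can absorb a shift common to both arms, not an arm difference that grows with window length.

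**Stronger readings that the documents do not support.** A reader might infer that quit attempts have no by-arm analysis at all. Section 11.0 has both a by-condition description and a between-arm HLM. A reader might also infer that quit duration will be compared only among those who attempted. No passage plans that; the plan is merely silent on the value for people with no attempt. Nor do the documents show that a missed survey lengthens the next record: that follows only if the previous follow-up means the previous completed one, which is left open.

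**Conclusion.** The point holds in a limited form. A linear model with no exposure term is the wrong stated method for outcomes whose records span about 7 and then about 28 days. If per-survey records are modelled, the absolute arm difference and its trend are distorted: on the 12-week reading, a jump from 2.8 to 10.4 points and an apparent growth of about 0.55 points per week with no change in behaviour. The trend figure further assumes that an arm difference in linear time is fitted; section 11.0 speaks of effects over time but lists only a main effect of time. The size rests on a constant attempt rate, complete surveys and an assumed period. The relative effect is little affected under those conditions.

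The second half needs no such assumptions. The 40% versus 15% rate has no period, and no stated analysis returns the per-arm proportion over a defined period. For a trial meant to supply an effect size, that should be settled before analysis. This is a pilot that disclaims full power, so the consequence falls on the usefulness of the estimate rather than on a confirmatory claim.

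**What to change.** 1. **Repeated quit-attempt data.** Use a Poisson or negative-binomial mixed model, or GEE, with log(days covered) as offset. Alternatively, cut the timeline calendar into equal windows before modelling.
2. **The design quantity.** State the period for the 40%/15% rate. Report that proportion by arm in all randomised participants as a risk difference with 95% CI, for example any attempt from baseline to Week 12.
3. **Missing surveys.** Add a rule to go with item 2, stating first whether recall runs from the previous scheduled or the previous completed survey. Section 11.0 itself expects gaps: "Considering the relatively small sample, possible missing data, and repeated measures".
4. **Leave the rest.** Keep HLM for the BDI-II and the Contemplation Ladder.

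The cost is plan wording and a little more analysis work. The timeline followback is already scheduled at every follow-up, so no new data collection is needed.

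### The plan does not fix which treatment contrast the HLM reports, and the terms it names, taken alone, give an average over visits whose size depends on the time course

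*Combined protocol and SAP*

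**What the plan says.** Section 1.0 (Hypotheses) predicts that participants given Goal2Quit+NRT Sampling, compared with TAU, "will have greater (numerically, if not statistically) decreases in depressive symptoms". Aim 3 in the same section and the opening of Section 11.0 both give an effect size estimate as a main purpose of the RCT.

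Section 10.0 has participants "complete follow-ups weekly for 8 weeks, with an additional follow-up at Week 12", and adds: "The BDI-II will be administered at all time points to determine change in symptoms". The schedule table agrees: BDI-II at baseline, Weeks 1 to 8 and Week 12. The PHQ-8 appears at screening only. The Contemplation Ladder, which measures motivation and confidence, is also taken at baseline and at every follow-up.

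Section 11.0 first describes the work as a "descriptive analysis of changes over time in depressive symptoms and cigarette smoking by condition". It then says "we will fit the longitudinal data with Hierarchical Linear Modeling (HLM) to fully use available data", and that intervention effects on the smoking-related outcomes and "depressive symptoms over time will be examined using HLM". The model terms follow: "Planned covariates will include sex and baseline levels of depression and nicotine dependence as well as the main effect of time".

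Nothing else in the document describes the model. It does not mention a condition-by-time term, continuous or categorical time, the week at which the arms are compared, the instrument meant by baseline depression, or whether the baseline measurement is also an outcome row.

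**The concern.** A hypothesis about greater decreases can be answered in at least three ways: a difference in slopes, a baseline-adjusted difference at a named week, or a baseline-adjusted difference averaged over follow-up. These are different quantities, and the plan does not choose. Taken at face value, the listed terms plus condition give the third. If the baseline row is also kept as an outcome, the average includes an occasion at which randomisation makes the expected difference zero.

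The choice matters more here than in many pilots because the number itself is the product. If the contrast is left open, the effect size passed to a larger trial depends on a modelling decision that could be made after the data are seen, and a reader of the result could not tell which quantity it is.

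There is a related gap for motivation and confidence. Their own baseline values are collected but are not among the listed covariates.

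**Working it through.** **Inputs from the document.** Visits at Weeks 0 to 8 and 12, so 10 occasions, 9 of them after baseline (Section 10.0 and its table). Arms of 100 and 50 (Section 11.0). The plan gives no BDI-II effect, SD, correlation or power to reproduce. Its only power figure, 60%, is for quit attempts at 40% against 15%, and this point does not depend on it.

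**Assumptions.** The time course, SDs and true differences below are illustrative. Power uses two-sided 5%, which the plan does not state.

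**1. Listed terms only, no interaction.** With complete data and a random intercept, the condition coefficient is the plain mean of the visit-specific differences.
- Effect constant from Week 1: 9/10 = 0.90 with the baseline row; 9/9 = 1.00 with post-baseline rows only.
- Effect growing linearly to Week 12: the weeks sum to 0 + 1 + … + 8 + 12 = 48. As a share of the Week 12 effect this is 48/(12 × 10) = 0.40 with the baseline row, and 48/(12 × 9) = 0.444 without it.

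The baseline row alone costs a factor of 0.9. The rest of the shortfall under linear growth comes from averaging, so dropping that row does not remove it.

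**2. Linear condition-by-time term instead.** Mean week = 48/10 = 4.8. Sum of squared weeks = 204 + 144 = 348, so Sxx = 348 − 10 × 4.8² = 117.6. For an effect of 1 at every visit after baseline, the cross-product is 48 − 9 × 4.8 = 4.8. The fitted 12-week change is 12 × 4.8/117.6 = 0.49 of the true effect. Under linear growth the same term recovers the whole effect.

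**3. Simulation check.** 400 trials per scenario, 100:50, assumed SD 10, true difference 5, within-person correlation 0.5 or 0.7, dropout 0% or 20%.

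| True course | Main effect, baseline row in | Main effect, post-baseline only | 12 × linear interaction |
|---|---|---|---|
| Constant | 4.35–4.48 | 4.93–4.98 | 2.33–2.64 |
| Linear to Week 12 | 1.82–2.03 | 2.06–2.25 | 4.95–5.07 |

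Under linear growth, power was 0.58–0.74 for the main effect and 0.91–1.00 for the interaction. Under a constant effect it was about 1.00 and 0.37–0.64. Neither simple choice is safe under both courses. Including the baseline row barely changes power (0.60 against 0.62 at correlation 0.5 with complete data under linear growth), because the estimate and its standard error shrink together.

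**4. Baseline-adjusted contrast at a named week.** Assumed example: 4-point difference at Week 12, person SD 7, residual SD 6, so variances 49 and 36, total 85.
- Week 12: variance given baseline = 85 − 49²/85 = 56.75; × (1/100 + 1/50) = 1.70; SE 1.30; 4/1.30 gives power of about 87%.
- Average of the nine follow-ups: 49 + 36/9 − 49²/85 = 24.75; × 0.03 = 0.743; SE 0.86.
- Listed terms with the baseline row, linear growth: estimate 0.40 × 4 = 1.6; SE 0.9 × 0.86 = 0.78; power about 54%.

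In 4,000 simulated complete-data trials per course, the Week 12 contrast returned −4.05 (linear) and −4.01 (constant) against a true −4. It therefore recovers the named-week effect under both courses. The cost is precision: SE 1.30 against 0.86 for the average.

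**The case against.** The strongest reply is that Section 11.0 lists covariates, not a full model. The list leaves out condition itself, so it cannot be complete. The surrounding sentences speak of effects and changes over time by condition, and a main effect of time is exactly what accompanies a tested interaction. This stands. A reader might infer that the plan rules out a condition-by-time term, but the text leaves it unstated.

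A reader might also infer that the baseline BDI-II is used on both sides of the model. The BDI-II is the depression scale in the baseline column, and nothing removes that row from the outcome, so this is possible. It is nevertheless an inference from an assessment schedule.

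Third, with post-baseline rows only, the condition main effect is a legitimate baseline-adjusted difference in mean decrease. That also stands.

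Fourth, one might read the 40% figure as showing that the estimate is biased toward zero in general. It does not. The two-week NRT supply and a quit date suggested within three weeks make an early effect plausible. Suppose, as an illustration, the effect is full in Weeks 1 to 4 and falls linearly to half by Week 12. The visit values sum to 4 + 0.9375 + 0.875 + 0.8125 + 0.75 + 0.5 = 7.875, so the ten-visit average is 0.79 of the peak against 0.50 at Week 12, and the average overstates the Week 12 effect.

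Finally, squaring 1/0.40 might suggest a next trial about six times too large. That requires a growing effect and a time-averaged difference put into a single-visit design with single-visit variance. The document names neither Week 12 nor the BDI-II as the basis for sizing that trial.

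What remains is that the contrast and the role of the baseline value are open, in a trial whose purpose is that estimate. The pilot status and descriptive focus lower the urgency but do not supply the missing definition.

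**Conclusion.** The point holds as an under-specified contrast that should be settled before analysis. It is not a demonstrated bias. The named terms, taken alone, yield a visit-averaged condition effect. Under the constant and linear-growth courses, that coefficient lies between about 40% of the Week 12 effect (linear growth, baseline row included) and 100% (constant effect, post-baseline rows only). A fading effect would take it above 100%. A linear interaction would understate an early constant effect by about half. The shares in steps 1 and 2 follow from the visit schedule, given the assumed time course, complete data and a random intercept. The standard errors and powers rest on assumed SDs and differences.

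This is more than a missing detail, because each of the two obvious ways of filling the gap gives an effect size that depends on an unknown time course, while a simple alternative does not.

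**What to change.** Write the model into Section 11.0.

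- **Repeated continuous outcomes (BDI-II, motivation, confidence).** Model the post-baseline values at Weeks 1 to 8 and 12 on condition, categorical week, condition by week, the baseline value of that same outcome, sex and baseline nicotine dependence, with within-person correlation.
- **Baseline depression.** State which instrument is meant. Keep it as a covariate in the motivation and confidence models. Do not use the baseline value of an outcome as both an outcome row and a covariate.
- **Contrasts.** Name one week in advance as the main contrast. Report the Week 8, Week 12 and average-over-follow-up contrasts, each with a 95% CI, so that the larger trial can be sized on whichever quantity it will use.
- **Quit attempts.** Handle these in a separate model suited to a binary outcome.

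The cost is wording only; data collection and software do not change. Nine categorical weeks need 8 week terms and 8 interaction terms in place of one linear time term, so 15 more parameters. If the effect really is constant, a single-week contrast is less precise than the average, which is a reason to report both.
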